7.6 VITAL SIGNS, HEIGHT AND WEIGHT

The following will be collected:

- Vital signs:
 - Seated blood pressure (taken after the subject has been seated for at least 5 minutes)
 - Pulse
 - Temperature (oral or tympanic)
 - Respiratory Rate
- Height (at Screening Visit only) and Weight
- BMI (derived from the height and weight measurements).

7.7 PHYSICAL EXAMINATION

The physical examination will include routine examinations for the following:

- Head, Ears, Eyes, Nose, Throat (HEENT)
- Abnormalities of the extremities
- Neurologic abnormalities
- Heart/cardiovascular abnormalities
- Musculoskeletal abnormalities
- Dermatologic abnormalities
- Any other body system for which an abnormality is noted and which, in the opinion of the Investigator, is relevant to the safety of the subject or could impact safety or efficacy results for the subject; i.e., the abnormality is clinically significant.

Each abnormality will be recorded and the Investigator will record an assessment of its clinical significance.

7.8 ECOG PERFORMANCE STATUS

The Eastern Cooperative Oncology Group (ECOG) performance status will be documented at screening, at the first visit of each treatment cycle, and at End of Treatment (EOT) visit.

Table 7-1: ECOG Performance Status Scale

Grade	Description
0	Asymptomatic; Fully active, able to carry on all pre-disease performance without restriction
1	Symptomatic but completely ambulatory; Restricted in physically strenuous activity but ambulatory and able to carry out work of a light or sedentary nature, e.g., light house work, office work
2	Symptomatic, <50% in bed during the day; Ambulatory and capable of all selfcare but unable to carry out any work activities. Up and about more than 50% of waking hours
3	Symptomatic, >50% in bed, but not bedbound; Capable of only limited selfcare, confined to bed or chair more than 50% of waking hours
4	Bedbound; Completely disabled. Cannot carry on any selfcare. Totally confined to bed or chair
5	Dead

* As published in Am. J. Clin. Oncol.: *Oken, M.M., Creech, R.H., Tormey, D.C., Horton, J., Davis, T.E., McFadden, E.T., Carbone, P.P.: Toxicity And Response Criteria Of The Eastern Cooperative Oncology Group. Am J Clin Oncol 5:649-655, 1982.* The Eastern Cooperative Oncology Group, Robert Comis M.D., Group Chair.

7.9 ELECTROCARDIOGRAM (ECG)

A resting supine 12-lead ECG will be conducted at the Screening Visit (SV), at baseline (C1D1), and at End of Treatment (EOT) visit. A 12-lead EKG will be repeated during the study only if clinically indicated and at the discretion of the treating physician. The results will be evaluated by the Investigator. The following parameters will be recorded: ventricular rate (beats per minute), PR interval (msec), QRS interval (msec), QT interval (msec), and QTc interval (msec). Additionally, the Investigator will record the overall results of the ECG reading as either normal or abnormal, and as either not clinically significant or clinically significant. If abnormalities are observed, each will be recorded.

7.10 TOXICITY ASSESSMENT

Any subject who receives at least one dose of study therapy will be evaluable for toxicity endpoints. Each subject will be assessed for the development of toxicity according to the timeframe referenced in the Schedule of Events table. Toxicity will be assessed according to CTCAE v 5.0 criteria. Refer to [Section 3](#) for the assessment criteria for dose limiting toxicity under Phase Ib of the study. Also

refer to [Table 6-3](#) and [Table 6-4](#) for the dose modification and management of leronlimab (PRO 140) and carboplatin for any toxicity.

All subjects will be followed for adverse events for 30 days after last dose of leronlimab (PRO 140) and carboplatin, or until the subject starts a new treatment, whichever occurs first.

Subjects who discontinue treatment for unacceptable adverse event(s) will be followed until resolution or stabilization of the adverse event (i.e. the grade is not changing). If a subject stops treatment due to unacceptable adverse event(s) but has not demonstrated disease progression, then the subject will be followed with imaging studies every 9 weeks until the time of progression radiographically according to RECIST v1.1 criteria.

7.11 CLINICAL LABORATORY ASSESSMENTS

Blood samples will be collected for analysis of the following parameters:

- Biochemistry and Complete Blood Count (CBC) Parameters: At Screening and Day 1 of each treatment cycle and at the end of treatment (EOT).
- Serum pregnancy test (for female subjects of childbearing potential): At Screening
- Urine pregnancy test (for female subjects of childbearing potential): At Day 1 of each treatment cycle
- CTCs PD-L1/CCR5 Analysis: At Day 1 of each treatment cycle and at the end of treatment (EOT).
- CTC and CAMLs Analysis: At Day 1 of each treatment cycle and at the end of treatment (EOT).

All laboratory reports will be reviewed by the Investigator. Abnormal results that are considered by the Investigator to be clinically significant, will be recorded as adverse events. If in the Investigator's judgment, in order to make the determination of clinical significance the testing may be needed to be repeated. Validated, quality-controlled laboratory data will be transferred to the main database for analyses.

Table 7-2: Central Lab Parameters

CBC Parameters	Biochemistry Parameters	Urinalysis
Hemoglobin	Liver Function Tests	pH
Hematocrit	Total Bilirubin	Appearance
RBC count	Direct Bilirubin	Color
WBC count	Alkaline Phosphatase (ALP)	Specific gravity
WBC Differential	Alanine Aminotransferase (ALT) (or SGPT)	Turbidity
Absolute lymphocyte count	Aspartate Aminotransferase (AST) (or SGOT)	Ketones
Absolute neutrophil count	Albumin	Bilirubin
Platelet count	Total Protein	Blood
Miscellaneous		Glucose
Serum pregnancy test	Renal Function Tests	Protein
Urine pregnancy test	blood urea nitrogen (BUN)	Nitrites
(for female subjects of childbearing potential)	Creatinine	Urobilinogen
Tissue for CCR5 expression (archival or fresh biopsy)	Electrolytes	Leukocyte esterases
Tissue for PD-L1 expression (archival or fresh biopsy)	Sodium	Microscopic exam includes bacteria, cast, crystals, epithelial cells, RBC and WBC.
CTCs PD-L1/CCR5	Potassium	
CTC CAMLs	Chloride	
	Calcium	
	Bicarbonate	
	Other:	
	Glucose, Random, Serum	

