- d. The occurrence in any subject of a life-threatening SAE whose causal relationship to leronlimab (PRO 140) is judged to be probable or definite
- e. The occurrence of one or more non-life-threatening SAEs whose causal relationship to leronlimab (PRO 140) is judged to be definite
- f. The occurrence, in one or more subjects, of Grade 4 laboratory abnormalities, judged to be probably or definitely related to receipt of leronlimab (PRO 140)
- g. The occurrence of hematologic and non-hematological adverse events, judged to be possibly, probably or definitely related to receipt of leronlimab (PRO 140) based on previous clinical experience and that are of CTCAE Grade 3 or greater severity. Permissible exceptions to this rule include Grade 3 fatigue of less than one week duration, and Grade 3 nausea, vomiting, and diarrhea that resolve within 48 hours following institution of appropriate supportive care.
- h. Hy's law
- i. Neutropenic fever
- j. Grade 4+ neutropenia or thrombocytopenia >7 days
- k. Grade 3+ thrombocytopenia with bleeding
- l. Grade 3+ electrolyte abnormality that lasts >72 hours, unless the patient has clinical symptoms, in which case all grade 3+ electrolyte abnormality regardless of duration should count as a DLT. Grade 3+ amylase or lipase elevation NOT associated with symptoms or clinical manifestations of pancreatitis does not need to be counted as a DLT
- m. For patients with hepatic metastases, AST or ALT >8xULN or AST or ALT >5x ULN for ≥ 14 days

If any of the SAEs or DLTs outlined above have occurred, the Data Safety Monitoring Board (DSMB) will conduct an independent review of the data and make a final decision for dose escalation to the next cohort.

The dosing regimen for each cohort is as follows:

- Cohort A: 350 mg leronlimab (PRO 140) SC weekly + AUC 5 Carboplatin every 3 weeks
- Cohort B: 525 mg leronlimab (PRO 140) SC weekly + AUC 5 Carboplatin every 3 weeks
- Cohort C: 700 mg leronlimab (PRO 140) SC weekly + AUC 5 Carboplatin every 3 weeks

Leronlimab (PRO 140) is administered as subcutaneous injection in the abdomen weekly. A total of 350 mg, 525 mg, or 700 mg (175 mg/mL) is delivered as two injections on opposite sides of the abdomen. The 350 mg dose will be delivered as two injections of 1 mL each, 525 mg dose will be delivered as two injections of 1.5 mL each and 700 mg dose will be delivered as two injections of 2 mL each.

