Note: All leronlimab (PRO 140) SC weekly injections at Cycle 1 (Days 1, 8, and 15) and at Day 1 of subsequent cycles must be administered at clinic. The remaining study treatment injections at Day 8 and Day 15 (beyond Cycle 1) may be self-administered by subjects at home after proper training by a healthcare professional.

Subjects will be allowed to continue treatment under subsequent treatment cycles until any one of the following occurs: progressive disease or unacceptable toxicity or withdrawal of consent.

(4) Follow-Up Period: An End of Treatment (EOT) visit will be conducted 30 (\pm 3) days after the last treatment visit (i.e., after last dose of leronlimab (PRO 140) and carboplatin). Additionally, follow-up will be done for survival status, by clinic visits or phone or another method of contact, every 3 months (\pm 1 month) for 2 years after treatment discontinuation or until death, whichever occurs first.

Figure 4-1: Study Flow Diagram

[figure not shown]

Table 4-1: Schedule of Assessments

Tests and Assessments		Screening Period						Treatment Period						Follow-up Period	
Visit	Day(s)	Treatment Cycle 1 (21 days)			Treatment Cycle 2 (21 days)			Additional Treatment Cycles			EOT	Survival Follow-ups			
		Pre-Screening Visit [1]	Screening Visit	C1D1	C1D8	C1D15	C2D1	C2D8	C2D15	CXD1	CXD8	CXD15			
Window		Within 28 Days from Screening visit	Day 1	Day 8	Day 15	Day 22	Day 29	Day 36							
Informed Consent [2]		X	X												
Demographics and Baseline Disease Char.		X													
Medical and Medication History [3]		X	X												
Vital Signs [4]		X	X	X	X	X	X	X	X	X	X	X	X	X	X
Height and Weight		X	X[5]												
Physical Exam		X	X	X[6]	X	X[6]	X	X[6]	X	X[6]	X	X[6]	X	X	X
ECOG Performance Status		X	X												
Electrocardiogram, 12-lead [7]		X	X												
Toxicity assessment (post treatment)			X												
Tumor Imaging Assessment [8]			X												
Complete Blood Count [9]		X	X[25]												
Biochemistry [10]		X	X[25]												
Urinalysis [11]		X	X[25]												
Serum Pregnancy test [12]		X													
Urine Pregnancy test [12]			X												
Eligibility Assessment		X	X	X											
Enrollment / Cohort Assignment		X													
Blood sample collection for CTCs PD-L1 /CCRS Analysis [13]			X												
Blood sample collection for CTC and CAMLs Analysis [14]			X												
Tissue for CCR5 (archival or fresh biopsy)			X[15]												
Tissue for PD-L1 expression level			X[16]												

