- [25] Can be performed within 3 days prior to each cycle start.

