4.3 TREATMENT PERIOD

Subjects who meet all eligibility criteria, as per data gathered from Screening Period are to be treated. All subjects who fail to meet eligibility criteria will be considered screen failure and exit the study without further evaluation

Phase Ib

The dose finding portion of study will follow a “3+3” design. The maximum sample size for this portion of the study is 18 subjects that will be followed by treatment according to the schedule described above starting on Cycle 1, Day 1.

Phase II

The maximum sample size for this portion of the study is 30 subjects that will be followed by treatment according to the schedule described above starting on Cycle 1, Day 1.

During the Phase Ib and Phase II of the study, treatment may continue until one of the following criteria applies:

- Disease progression,
- Intercurrent illness that prevents further administration of treatment,
- Unacceptable adverse event(s), or
- Withdrawal of consent

Each treatment cycle consists of 21 days. Leronlimab (PRO 140) will be administered subcutaneously weekly on Days 1, 8, and 15 in combination with carboplatin AUC 5 on Day 1 of each cycle (every 21 days). Day 1 of Cycle 2 begins at Day 22.

4.3.1. Treatment Cycle 1, Day 1

The following assessments will be performed at the first treatment visit of Cycle 1:

- Concomitant medications assessment (see [Section 7.5](#)),
- Vital Signs and body weight measurement (see [Section 7.6](#)),
- Physical examination, including evaluation of all body systems (see [Section 7.7](#))
- ECOG Performance Status (see [Section 7.8](#))

- 12-lead Electrocardiogram (see [Section 7.9](#))
- Collection of lab specimens (see [Section 7.11](#)) for
 - Complete blood count
 - Biochemistry
 - Urine pregnancy test, for female subjects of childbearing potential.
 - Urine sample for urinalysis parameters
 - CTCs PD-L1/CCR5 analysis
 - CTC and CAMLs analysis

Note: Complete blood count, biochemistry and urinalysis can be performed within 3 days prior to each cycle start.

- Leronlimab (PRO 140) Administration (see [Section 6.1.3](#))
- Carboplatin Administration (see [Section 6.2.5](#))
- Post Injection Site Evaluation (performed by Investigator) (see [Section 7.13](#))
- Toxicity assessment (see [Section 7.10](#)) and Review of Adverse Events (see [Section 9](#))

4.3.2. Treatment Cycle 1, Day 8 & Day 15

The following assessments will be performed at during the remaining visits (Day 8 and 15) in the first treatment cycle:

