6.2.11. Carboplatin - Nursing implications

1. Aluminum displaces platinum from the carboplatin molecule, resulting in the formation of a black precipitate and loss of potency. Carboplatin solutions should not be prepared with needles, syringes, catheters, or IV administration sets containing aluminum parts that might be in contact with the drug.
2. Monitor CBC and platelet count at least every 21 days or earlier if warranted per institutional standard of care.

3. Premedicate with antiemetics – prophylaxis with a 5HT3 receptor antagonist and dexamethasone (+/- aprepitant) is standard.
4. Monitor fluid status – maintain adequate hydration.
5. Assess skin/mucous membranes.
6. Assess for signs of peripheral neuropathy – coordination, sensory and hearing loss.

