8.5 INTERIM ANALYSIS

No interim analysis (IA) will be performed for efficacy. There will be a safety review, once all three (or six) subjects from each cohort complete the DLT evaluation period (defined as cycle 1 or the first 21 days of treatment).

The Sponsor's Medical Monitor, CRO Medical Monitor and study investigators must be satisfied with data obtained in Cohort A before allowing subsequent enrollment of Cohort B. Likewise, they must be satisfied with data obtained in Cohort B before allowing subsequent enrollment in Cohort C.

In addition, should any of the following events occur in any cohort during the DLT evaluation period, the Data Safety Monitoring Board (DSMB) will meet to review available study data and make a final decision for dose escalation to the next cohort:

- a. Death in any subject in which the cause of death is judged to be possibly, probably or definitely related to leronlimab (PRO 140)
- b. The occurrence in any subject of an anaphylactic reaction to leronlimab (PRO 140)
- c. The occurrence in any subject of a severe local injection site reaction (Grade 3 which is not resolved or recurs; or Grade 4) that precludes administration of consecutive leronlimab (PRO 140) doses.
- d. The occurrence in any subject of a life-threatening SAE whose causal relationship to leronlimab (PRO 140) is judged to be probable or definite
- e. The occurrence of one or more non-life-threatening SAEs whose causal relationship to leronlimab (PRO 140) is judged to be definite
- f. The occurrence, in one or more subjects, of Grade 4 laboratory abnormalities, judged to be probably or definitely related to receipt of leronlimab (PRO 140)
- g. The occurrence of hematologic and non-hematological adverse events, judged to be possibly, probably or definitely related to receipt of leronlimab (PRO 140) based on previous clinical experience and that are of CTCAE Grade 3 or greater severity. Permissible exceptions to this rule include Grade 3 fatigue of less than one week duration, and Grade 3 nausea, vomiting, and diarrhea that resolve within 48 hours following institution of appropriate supportive care.
- h. Hy's law
- i. Neutropenic fever
- j. Grade 4+ neutropenia or thrombocytopenia >7 days
- k. Grade 3+ thrombocytopenia with bleeding

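### Phase Ib DLT criteria that turn on how long a laboratory abnormality lasts cannot be confirmed from the bloods scheduled in Cycle 1

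*Protocol*

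**What the plan says.** **DLT list (Protocol Section 3; repeated in the synopsis, Sections 8.5 and 12, and SAP Section 4).** Criterion j is "Grade 4+ neutropenia or thrombocytopenia >7 days". Criterion l counts a Grade 3 or higher electrolyte abnormality once it exceeds 72 hours, or at any duration if the patient has symptoms. Criterion m reads "For patients with hepatic metastases, AST or ALT >8xULN or AST or ALT >5x ULN for ≥ 14 days". Only its second branch carries a duration.

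**Window.** Protocol Section 8.5 and SAP Section 4 place the safety review after all subjects in a cohort "complete the DLT evaluation period (defined as cycle 1 or the first 21 days of treatment").

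**Laboratory schedule.** Protocol Section 7.11 gives "Biochemistry and Complete Blood Count (CBC) Parameters: At Screening and Day 1 of each treatment cycle and at the end of treatment (EOT"). Table 4-1 footnote 25 adds a sampling allowance: "Can be performed within 3 days prior to each cycle start". Section 4.3.2 opens its list with "The following assessments will be performed at during the remaining visits (Day 8 and 15) in the first treatment cycle"; the items are medications, adverse events, vital signs, a symptom-based examination, the injection, the injection-site check and the pain scale. There is no blood sample. The SAP schedule (Appendix 1) shows blood count and biochemistry at Screening, C1D1, C2D1, later Day 1 visits and EOT only.

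**Provision for earlier sampling.** Section 6.2.11 says "Monitor CBC and platelet count at least every 21 days or earlier if warranted per institutional standard of care". Section 4.5 leaves assessments at unscheduled visits to the investigator. Table 6-4 asks for weekly counts only after a cytopenia has been found.

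**The concern.** The DLT count in Cycle 1 is the Phase Ib primary endpoint, and Section 3 allows escalation only once the investigator has determined that no listed event has occurred. For a patient without symptoms, that determination about criterion j, asymptomatic l and the 5xULN branch of m needs laboratory values at more than one time. The schedule supplies one post-dose time point, at or just after the end of the window.

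The gap is somewhat wider than the three duration rules. Laboratory events under criteria f and g, and AST/ALT above 8xULN, need no minimum duration. They too are not reliably detected if they arise and resolve between C1D1 and C2D1 without symptoms.

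Protocol Section 1.3.2 identifies marrow suppression as the toxicity that limits carboplatin dosing, so an asymptomatic cytopenia is a plausible event. Criterion j carries no clause requiring attribution to leronlimab. The dose selected goes to 30 Phase II patients, and patients in lower cohorts may be moved up to it.

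**Working it through.** **1. The plan's own figures.** Three levels of up to six patients give 3 × 6 = 18, the stated Phase Ib maximum. One DLT in six is 1/6 = 16.7%, the stated 17%. Both reproduce.

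**2. What the scheduled samples can document.** Showing that an abnormality lasted longer than a limit needs two abnormal samples at least that far apart. Between the first dose and C2D1 there is one post-dose sample, so the longest span that scheduled bloods can document in Cycle 1 is 0 days. The limits are over 3 days, over 7 days and at least 14 days. None can be met.

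**3. How often the one sample would still find a Grade 4 episode.** Assumption: onset is equally likely on each of Days 2 to 14, the 13 start days for which an eighth day falls within Day 21. An episode of length L starting on day s is over before a draw on day D if s + L − 1 < D.

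| Episode length | Over before a Day 22 draw | Over before a Day 19 draw |
|---|---|---|
| 8 days | 13 of 13 | 10 of 13 |
| 10 days | 11 of 13 | 8 of 13 |
| 14 days | 7 of 13 | 4 of 13 |

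An episode still present at the draw is seen, but without its onset or duration.

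**4. Effect on the 3+3 rule (illustration).** With q the observed DLT probability, the chance of escalating past a level is P = (1 − q)³ + 3q(1 − q)² × (1 − q)³. Both wordings of the 3+3 rule in Section 3 give this P. Set q = true rate × share seen. The true rate (33%) and the share seen are assumptions; the documents give neither.

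- All seen, q = 0.33: 0.3008 + 0.1337 = 0.434.
- A quarter unseen, q = 0.2475: 0.4261 + 0.1792 = 0.605.
- Half unseen, q = 0.165: 0.5822 + 0.2009 = 0.783.

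At a true rate of 40% the three values are 31%, 49% and 71%; at 50% they are 17%, 35% and 60%. If all three levels had a true rate of 33%, the chance that all pass is 0.434³ = 8%, 0.605³ = 22% or 0.783³ = 48%.

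**5. What samples at the existing Day 8 and Day 15 visits would add.** Take an episode lying wholly within Days 1 to 22, with uniform onset.

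- Eight days: onset ranges over 13 days. The current schedule meets 0% of episodes (Day 22 draw) to 3/13 = 23% (Day 19 draw). With Day 8 and Day 15 added, every such episode meets at least one sample.
- Four days: onset ranges over 17 days. The current schedule meets 0% to 3/17 = 18%. With the added draws it is 8/17 = 47% to 11/17 = 65%.

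Weekly draws therefore detect the longer events but seldom prove a duration by themselves; that needs repeat samples after a first abnormal value.

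**The case against.** Several points on the other side are sound.

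- **Not every branch needs a duration.** Symptomatic electrolyte events and AST/ALT above 8xULN count without one. Neutropenic fever and thrombocytopenia with bleeding present clinically and are not hidden in the same way.
- **Sites may look earlier.** Sections 6.2.11 and 4.5 permit it, Section 7.11 allows repeat testing, and adverse events are reviewed on Days 8 and 15. A reader might infer that these DLTs can never be seen. The documents do not support that: sampling is permitted but not required, so detection can differ between the up to five sites. Section 6.2.11 also covers blood counts only, not biochemistry.
- **A C2D1 value can inform the decision.** Section 3 requires follow-up of at least three weeks before escalation, so a Day 22 result may be available at the review. Whether it counts formally in a 21-day window is not stated. Weekly counts under Table 6-4, if triggered by that sample, would time the event after Cycle 1 rather than within it.
- **Partial recovery may still show.** A count that has improved to Grade 3 by C2D1 is visible and, if judged at least possibly related to leronlimab, meets criterion g. The step 3 counts concern Grade 4 only.
- **Few silent DLTs may occur.** Carboplatin is fixed at AUC 5 in every cohort, and Section 1.3.2 expects no overlapping marrow effect and no major increase in carboplatin toxicity. This bears on the size of the effect. It does not close the gap, because Phase Ib exists to test that expectation.

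The SAP schedule is weak corroboration, since it differs from the protocol elsewhere (its scan timing, for example). The laboratory rows of Protocol Table 4-1 were not fully legible in the text available to me. Sections 7.11 and 4.3.2 carry the point.

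**Conclusion.** The point holds in this form. As scheduled, the Cycle 1 bloods cannot confirm criterion j, asymptomatic l or the 5xULN branch of m. They do not reliably detect silent laboratory events, including those under f, g and AST/ALT above 8xULN, that resolve before C2D1. This follows from the documents without any assumption about rates.

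The direction of the effect is also clear: a missed DLT can only move the 3+3 towards a higher MTD. Its size is not known. The rise from 43% to about 60% or 78% rests on an assumed 33% true DLT rate and an assumed quarter or half of DLTs unseen. A reader might infer that the MTD will be set too high; the documents do not support that, because they give no silent share and expect no overlapping marrow toxicity.

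**What to change.** Reconcile the DLT list with the Cycle 1 laboratory schedule in Protocol Sections 4.3.2 and 7.11, Table 4-1 and SAP Appendix 1, so that the planned Phase Ib bloods can detect and time the events that the list names. The Day 8 and Day 15 visits are an available opportunity: Section 4 requires that "All leronlimab (PRO 140) SC weekly injections at Cycle 1 (Days 1, 8, and 15") be given in clinic.

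The sponsor should also state:

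- whether the C2D1 pre-dose sample counts in the DLT window;
- how repeat sampling is arranged once a value reaches a threshold in j, l or m;
- how an abnormality of unknown duration is classified. No classification is proposed here, because Table 6-3 ties a DLT to permanent discontinuation of treatment, so this is a clinical rule for the sponsor to settle.

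Cost: a schedule amendment and, if both visits are used, up to 2 × 18 = 36 extra panels without extra routine visits. Some repeat draws would follow when a threshold value is found, possibly at unscheduled visits, because weekly sampling cannot resolve a 72-hour limit.
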